Study Cover Page

Official Study Title: Treatment of Prolonged Grief Disorder in Combat Veterans

NCT02283333

Protocol date: August 4, 2014

Data Analytic Plan

Baseline data were compared across groups using t-tests for continuous variables and chi-square tests for proportion variables to examine differences in demographic factors, pre-treatment symptom intensity (i.e., grief, depression, and PTSD), and co-variates that are particularly relevant to research with veterans (i.e., social support, time since death, and overall number of sessions completed). No differences in scores or proportionate representation were noted in terms of any demographic, baseline symptoms, or potential covariates. Next, repeated measures analysis of variance were conducted to determine the relative effectiveness of BATE-G vs. CT-G in terms of grief (i.e., ICG-R), depression (i.e., BDI-II) and PTSD (i.e., PCL-5) symptom outcomes. Although no covariation control (i.e., ANCOVA) was employed because covariates did not differ between groups. Baseline scores on primary dependent measures were included in the ANOVA model to test overall effects of time. The intent to treat (ITT) sample served as the primary analytic sample, and missing data were conservatively replaced through total sample mean substitution, which shares variance of missing data across groups and lessens likelihood of finding spuriously significant results. All analyses were repeated with the 'per protocol' sample, here defined as those who completed at least 5 of the 7 sessions specified in each treatment protocol. No differences in statistical significance were noted for any variable between ITT and per protocol samples, and thus the ITT sample data alone are reported.

Protocol

SIGNIFICANCE

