Randomization Procedures. A random size block randomization schedule will be generated. In Aggregate, participants will be randomly assigned (1:1) to one of the two study conditions. After determining eligibility, enrolled patients will be assigned to treatment groups by the Project Coordinator and research assistant using a web-based computer generated randomization scheme. Specifically, numbered, sealed envelopes containing a sheet of paper with the randomly generated condition assignment by the study statistical coordinator ([name]) will be created. After consent and assessment, the envelope for each participant will be opened to randomly assign the participant to his/her condition. The randomization results then will be recorded on the master tracking table by the research assistant (independent evaluators are blind), overseen by the Project Coordinator. Randomization will occur at the patient level. Once a patient is randomized and attends the first session, he or she will be entered into the study and included in the intent-to-treat analysis plan. The only members of the research team who will be aware of randomization assignment will be the project therapists, the Research Assistant, and the statistical analyst in charge of randomization.

Participant Payment. All participants will receive \$30 for the baseline assessment, \$30 for the post-treatment assessment, \$35 for the 3-month follow-up assessment, and \$45 for the 6-month follow-up assessment for a combined possible total of \$140. In some cases where financial difficulty associated with study completion can be mitigated by small increases in study payment, we request to do so, up to \$60.

Treatments

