Decision Point - Selection of the Comparison Condition: Two comparison treatment conditions were considered for this study: Shear et al.'s 15-20 session protocol for complicated grief vs. the treatment suggested by the VA / DoD in the Iraqi War Clinician Guide, 2nd ed. for VA populations. The former treatment has not been tested with Veterans, is not currently used in VA settings, and, if offered per protocol, represents a significant confound with respect to overall number of treatment sessions compared to the proposed 7 session experimental treatment. The latter treatment has not been empirically evaluated, but is specifically directed toward treatment of Veterans, is actually outlined on the VA's National Center for PTSD website is distributed to VA and DoD clinicians in the Iraq War Clinicians Guide, 2nd ed. and represents what should be, if VA recommendations were followed nationwide, the most commonly offered treatment. Thus, our decision balanced the advantages of (a) comparing our new treatment to a one that may well be effective but will rarely be offered, and if offered, rarely completed in VA settings, due to its complexity and length, vs. (b) comparing our treatment to one that is actually suggested and advised to be offered across VA settings. Setting aside the obvious problem of confound regarding number of sessions, we concluded that comparing our intervention to one that is not offered now, and is unlikely to be offered in the future would provide less direction to VA clinicians than comparing our treatment to what is actually being suggested, and more likely to be implemented in VA clinics the future, unless some equally rapid, easily disseminated alternative were demonstrated to be more effective. However, our decision was finalized by consistent findings that the modal number of mental health treatment sessions received by Veterans with mental health diagnoses was **one** (Cully et al., 2008; see also Gibbons et al., 2011). Thus, this treatment, albeit brief, is 7 times longer than the modal number of treatments typically received by Veterans. As such, we chose Cognitive Restructuring and Supportive Grief Counseling intervention, as suggested and outlined by the VA/DoD Iraq War Clinician Guide, 2nd edition, is far more representative of the type of treatment that might ever be used in the VA and by Veterans.

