Decision Point - Use of Televideo delivery of treatment sessions: We understand that, while preserving the 'typical' treatment content we are adding an innovation to the grief counseling approach suggested by the VA/DoD Clinician Guide insofar as the Cognitive Restructuring and Supportive Grief Counseling is here being delivered via televideo for sessions 2, 3, 4, 5, and 6. We felt it necessary to experimentally balance the delivery of services insofar as this technology is concerned because the PI's data from ongoing clinical trials indicates lower attrition and missed appointments in persons receiving home based televideo delivered treatment (e.g., in our current RCT of BATE-G for PTSD in Veterans, individuals in the televideo condition evinced 45.8% fewer missed appointments (Acieno, 2012)). As differential attrition was considered a greater threat to experimental validity than novelty of treatment delivery modality, and as the content of the control treatment is exactly that of typically offered bereavement supportive counseling, we feel that this decision is well justified.

Home-Based Televideo Procedures for Both Conditions: We will follow the VA

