Selected Axis I Mental Diagnoses	Structured Clinical Interview for DSM-5 (To Be released)	Clinician administered, gold standard; Dx: Major Depression, Panic Disorder, Generalized Anxiety Disorder, PTSD, Sub. Use Disorder. (Last version TBA)	Base, Post-Tx, 3 & 6 month

Depression	Beck Dep Inventory-II (Beck et al, 1996)	21 item self-report; high reliability and concurrent validity (Beck, Steer, & Brown, 1996)	Base, Post-Tx, 3 & 6 month
PTSD	PTSD Symptom Scale (Foa et al., 1993)	17 item self-report; 3 subscales. High reliability and concurrent validity (Foa et al., 1993)	Baseline, Post-Tx 3 & 6 month

Power Analysis. The primary longitudinal efficacy outcome variables are: intensity of PGD symptoms (ICG), and depression symptom severity (BDI) and PTSD (PCL) variables. In several studies of behavioral activation for mood disorders by Lejuez and colleagues (Hopko, Lejuez, & Hopko, 2004; Hopko et al., 2003; Lejuez et al., 2011, Lejuez, Hopko, & Hopko, 2001; MacPherson et al., 2010), effect sizes of .7 to 1.5 were obtained. In addition to behavioral activation, the present intervention also includes a video-based treatment for PTSD-like symptoms of complicated bereavement based on our existing treatment for PTSD in combat Veterans. In the pilot study, this treatment achieved an effect size of 0.7 on psychological outcomes, and .25-.3 on health outcomes. For comparing the longitudinal profile of continuous outcomes for the BATE-G versus Comparator groups across the study period [assuming 4 measurement time points, level of significance alpha=0.05, two-tailed comparison, correlation between pairs of measurements within subjects (interclass correlation) no larger than p=0.5], we estimate that with 44 subjects per group (88 total), we will have approximately 90% power to detect a standardized effect size of at least 0.35 (difference in comparison group means in units of standard deviation (sd)). For outcome variables having standard deviations (sd) in the range 5-15, for example, the raw effect sizes that can be detected range from approximately 2.3 to 6.9 raw units. To account for attrition during treatment (28%), and loss to followup (10-15%), we inflate the sample size accordingly to achieve a final sample size of approximately 140 subjects: 140 x 28% attrition = 101; 101 x 12% loss = 89 total participants completing all measures (note, ITT sample size will be 28% larger than power estimate requires, as treatment dropouts are included in ITT analyses).

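### If dropout is random and similar by arm, filling missing ITT scores with the total-sample mean shrinks the treatment difference: a true 0.35 SD at 6 months reads about 0.31 if treatment dropouts were assessed and 0.22 if not

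*Combined protocol and SAP*

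**What the plan says.** The Data Analytic Plan makes ITT the primary sample and states that "missing data were conservatively replaced through total sample mean substitution". Its reason is that sharing the filled values across groups "lessens likelihood of finding spuriously significant results". It does not say whether the mean is taken at each visit or pooled over visits. The same model also serves a pre-post question: "Baseline scores on primary dependent measures were included in the ANOVA model to test overall effects of time". The only other analysis is a per-protocol repeat in those who completed at least 5 of 7 sessions, reported as "No differences in statistical significance were noted for any variable between ITT and per protocol samples". No mixed model or multiple imputation appears.

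Under Randomization Procedures, once a patient is randomised and attends session 1, "he or she will be entered into the study and included in the intent-to-treat analysis plan". The Power Analysis expects 28% attrition during treatment and then 10-15% loss to follow-up, worked as 140 to 101 to 89. It counts treatment dropouts as part of the ITT sample.

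**The concern.** A value common to both arms carries no information about the difference between them, so filling pulls that difference toward zero. The plan presents this as a safeguard. It would be one only if the arm tests otherwise rejected too often.

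The direction matters because the comparator is an active treatment. In the section on selecting the comparison condition, the plan says the recommended treatment is the more likely one to be used in VA clinics "unless some equally rapid, easily disseminated alternative were demonstrated to be more effective". An estimate biased toward no difference therefore favours the comparator.

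**Working it through.** **Inputs.** From the Power Analysis: N = 140 (70 per arm at 1:1), four visits, within-subject correlation 0.5 (the plan's upper limit), reference effect 0.35 SD, 28% attrition, 12% later loss. My assumptions: unit variance, equal correlation between visits, the same true difference at all three post-baseline visits, and random dropout at the same rate in each arm.

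**1. The plan's own figure.** 140 x 0.72 = 100.8, and 100.8 x 0.88 = 88.7, which rounds to the stated 89. The fraction missing at 6 months is 1 - 89/140 = 36.4% if treatment dropouts are never assessed. It is 12% if all of them are assessed and only follow-up loss is missing. If half are assessed it is 1 - 0.86 x 0.88 = 24.3%.

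**2. Attenuation.** With a fraction m missing in each arm, expected difference = true difference x (1 - m).
- Assessed: 0.35 x 0.88 = 0.308 (0.315 to 0.298 for 10% to 15% loss).
- Unassessed: 0.35 x 0.636 = 0.22 (0.227 to 0.214 for 10% to 15% loss).
- Post-treatment: 0.35 x 1 = 0.35 if assessed, 0.35 x 0.72 = 0.25 if not.

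These are in original SD units. Filling also shrinks the SD: on the filled data's own SD the 6-month values are 0.33 and 0.28.

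**3. Interval coverage at 6 months.** SE of the filled difference = sqrt((2/70)(1 - m)).
- Unassessed: SE 0.135, bias 0.1275, which is 0.94 SE. Coverage = Phi(2.90) - Phi(-1.02) = 84%.
- Assessed: SE 0.159, bias 0.042, which is 0.26 SE. Coverage = Phi(2.22) - Phi(-1.70) = 94%.

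In simulation the sampling SD in the unassessed case is 0.136, so the SE is right for the filled estimate. The interval is simply centred on the wrong value.

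**4. Group-by-time power at 0.35 SD.** Noncentral F with 3 and 3(2n - 2) df, ncp = n x 0.375 x 0.35^2 / (1 - 0.5).
- Complete data, n = 70: ncp 6.43, power 55%.
- The 89 completers, n = 44.5: ncp 4.09, power 36%.

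These do not attempt to reproduce the plan's 90% with 44 per group. That is a separate question, and nothing here rests on it.

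**5. Simulation** of the two-way repeated-measures ANOVA, with dropout as in step 1:

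| | None assessed | Half assessed | All assessed |
|---|---|---|---|
| Missing at post / 3 / 6 months (%) | 28 / 36.4 / 36.4 | 14 / 24.3 / 24.3 | 0 / 12 / 12 |
| 6-month estimate of 0.35 | 0.22 | 0.26 | 0.31 |
| 95% CI coverage | 84% | 91% | 94% |
| Group-by-time power, mean substitution | 30% | 39% | 48% |
| Group-by-time power, mixed model, same terms | 44% | 48% | 52% |
| Time-test error, per-visit mean, no true change | 23% | 14% | 7-8% |

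With no true effect, the group and group-by-time tests reject 4.5-5.3% of the time in every case.

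**6. Time test.** Per-visit filling leaves the visit mean unchanged but counts filled values as data. At correlation 0.5, the nominal SE of the baseline-to-6-month change is sqrt(0.636) = 0.80 of its true size with dropouts unassessed. Error is then 2[1 - Phi(1.96 x 0.80)], about 12% for that contrast and 23% for the four-visit F test. With one pooled mean the error stays near 5%, but real change is understated.

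**The case against.** **The harm may be mild.** Dependent Measures & Interviewers says that all participants complete most measures at every visit, and Participant Payment pays all participants per assessment with no stated link to finishing treatment. Both lean toward the 12% case, with no shrinkage at post-treatment and coverage near 94%. The Power Analysis count of 89 with full measures leans the other way. Research Design and Methods complicates matters by describing 140 who complete treatment and follow-up. The 36% case cannot be taken as what happened.

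**Bias toward no difference is what conservative usually means in a superiority comparison.** That is fair for the direction of the estimate. It does not support the stated reason, because the arm tests hold about 5% without any such help.

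**The time-test error is remote.** It needs a per-visit mean, which the plan does not state, and no true change. The pilot grief change was 5.2 points against an SD of 1.3 x sqrt(26) = 6.6, or 0.78 SD. The time effect is also an uncontrolled pre-post test. This point is secondary.

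**The per-protocol repeat agreed.** This is partial reassurance. Only significance is said to agree; neither the estimates nor the handling of missing scores in that sample is given.

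**Two stronger readings fail.** A reader might infer that filling is always worse than dropping incomplete cases. It is worse only for the group-by-time test with dropouts unassessed (about 30% against 36%); the group test and the 6-month contrast are about equal. A reader might also infer that the rule hid a real benefit or led to a claim of equivalence. The documents give no arm result and claim no equivalence. If the arms differed significantly, attenuation does not threaten that conclusion.

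**Conclusion.** The concern stands in conditional form. With random dropout at similar rates by arm, the primary estimate is attenuated by the fraction missing: from 0.35 to about 0.31 or 0.22 SD at 6 months, depending on a fact that the documents do not give. The rule also costs group-by-time power relative to a mixed model, by 14 points in the worse case and 4 in the milder one. It gives no added protection against a spurious arm difference, and it does not inflate false-positive arm results either.

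The similar-by-arm assumption is reasonable. Delivery was matched across arms because "differential attrition was considered a greater threat to experimental validity than novelty of treatment delivery modality". If rates differ and the mean is per visit, the factor becomes the harmonic mean of the observed fractions: 72% and 55% observed gives 0.35 x 0.624 = 0.218, still toward zero. Dropout related to severity could move the bias either way. The documents give no model for it, so I claim no figure.

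This should be fixed: the primary estimate is biased under the plan's own expected attrition, and the remedy is inexpensive.

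**What to change.** Make the main reported analysis a likelihood-based mixed model for repeated measures on all observed scores. Keep baseline as one of the four outcome visits, with visit, treatment-by-visit and an unstructured covariance, so that treatment contrasts and the time test both remain available. Multiple imputation within arm from baseline and interim scores is an acceptable alternative.

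Report treatment contrasts with confidence intervals, and observed missingness by arm and visit, stating whether treatment dropouts were assessed. Because the Data Analytic Plan already reports results, label this a post-hoc correction and show it beside the existing analysis. Keep mean substitution as a sensitivity analysis, say whether the mean was per visit or pooled, and delete the conservative justification.

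The cost is a small re-analysis of data already held, in standard software. Intervals will be wider: a 6-month SE of about 0.18-0.20 instead of 0.135 if dropouts were unassessed. In that case the model's group-by-time error was about 6% in simulation with a plain Wald F test, so a small-sample correction is worth using.

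### Per-protocol results are left out because their significance matched ITT, but matching significance does not show matching effects and says little about missing data

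*Combined protocol and SAP*

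**What the plan says.** The Data Analytic Plan, on the opening page of the combined document, makes ITT the primary sample. For that sample, "missing data were conservatively replaced through total sample mean substitution", on the ground that this "lessens likelihood of finding spuriously significant results". The comparison of treatments is by repeated measures ANOVA for grief (ICG-R), depression (BDI-II) and PTSD symptoms (PCL-5).

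All analyses were repeated per-protocol, meaning in "those who completed at least 5 of the 7 sessions specified in each treatment protocol". The outcome of that repeat is one sentence. It begins "No differences in statistical significance were noted for any variable between ITT and per protocol samples" and closes "between ITT and per protocol samples, and thus the ITT sample data alone are reported".

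The Power Analysis section gives the planned losses: 28% attrition during treatment, then 10-15% loss to follow-up, worked through at 12%. It states that treatment dropouts stay in the ITT analysis.

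The documents give no per-protocol estimate or interval and no observed count of missing values by arm or visit. They do not say whether treatment dropouts were assessed, or how gaps inside the per-protocol set were handled.

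**The concern.** Two analyses can fall on the same side of 0.05 and still give different effects. Under this rule a result is left out because of its p-value, and the reader never sees whether the estimates differ.

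The imputation makes this more than a formality. Giving every missing patient in both arms the same value pulls the arm means together, and the constants add almost no variance while the sample size stays at its full value. The ITT estimate is therefore smaller, and its interval narrower, than the observed data alone would give. The per-protocol repeat is the only other analysis described that could reveal this, and it is judged on the one quantity that this imputation can leave almost unchanged.

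At stake is whether a reader can tell how far the primary result depends on the imputation.

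**Working it through.** **Inputs.** From the Power Analysis section: 140 enrolled, 28% attrition, 12% loss (range 10-15%), four time points, within-subject correlation 0.5, two-sided 0.05, effect size 0.35, pilot effect 0.7. From Randomization Procedures: 1:1 allocation, so 70 per arm. Assumptions not in the documents: dropouts have no data after baseline, they are the patients outside the per-protocol set, and losses are equal in the two arms.

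**Step 1: the plan's own chain.** 140 × 0.72 = 100.8 and 101 × 0.88 = 88.9. This reproduces "101 x 12% loss = 89 total participants completing all measures".

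**Step 2: missing share m.** Post-treatment m = 0.28. At follow-up m = 1 − 0.72 × 0.88 = 0.366. With 10% or 15% loss in place of 12%, the observed share is 0.72 × 0.90 = 0.648 or 0.72 × 0.85 = 0.612.

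**Step 3: effect on one visit.** Let D be the observed-data difference and s the within-arm SD.
- Difference after substitution: (1 − m) × D.
- Within-arm variance after substitution: about (1 − m) × s².
- SE after substitution: √(2(1 − m)s²/n). Observed-data SE: √(2s²/(n(1 − m))). Their ratio is 1 − m.

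Estimate and SE shrink by the same factor, so the t statistic barely changes.

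At follow-up with n = 70, s = 1 and D = 0.35:
- Observed SE = √(2/(70 × 0.634)) = 0.212, giving an interval about 0.84 wide.
- Substituted estimate = 0.634 × 0.35 = 0.22, SE = 0.634 × 0.212 = 0.135, interval about 0.53 wide.

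Simulation gives the same 6-month figures: 0.22 with width 0.53 for ITT, and 0.35 with width 0.84 for per-protocol. The significance call agrees in about 99.7% of trials or more for true differences from 0 to 0.7 SD. This near-identity needs the dropouts to be unassessed. If 25-50% of them are assessed and show no benefit, single-visit agreement falls to 78-86%.

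**Step 4: the planned model.** In the group-by-time test of the 2 × 4 ANOVA ("assuming 4 measurement time points"), dropouts keep their real baseline values, so the identity breaks. Simulated agreement per outcome (common improvement of 1 SD assumed; gaps inside the per-protocol set filled with its own mean):

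| True difference (SD) | Mean-substituted ITT vs per-protocol | Fully observed ITT vs per-protocol |
|---|---|---|
| 0 | 95% | 94% |
| 0.35 | 82% | 80% |
| 0.5 | 79% | 78% |
| 0.7 | 88% | 89% |

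Other runs agree to within about two points. Limiting per-protocol to complete cases lowers the first column slightly, to 94%, 79%, 76% and 86%. Agreement on all three outcomes together, with an assumed correlation of 0.6 between them, is 87%, 58-60%, 53% and 72%.

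**Step 5: how dropouts fared.** Take a true difference of 0.7 SD in those who stay. Post-treatment, mean-substituted ITT gives 0.72 × 0.7 = 0.50 in every case.
- Dropouts gain nothing from BATE-G: the true ITT difference is also 0.50.
- Dropouts keep the full benefit: the true ITT difference is 0.70.
- BATE-G dropouts do 1 SD worse than comparison dropouts: the true ITT difference is 0.72 × 0.7 − 0.28 × 1 = 0.22. Averaged over the three later visits, mean-substituted ITT gives (0.72 + 0.634 + 0.634)/3 × 0.7 = 0.46.

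In that last case mean-substituted ITT still matches per-protocol significance in 88% of simulated trials, whereas fully observed ITT data would match in only 28%.

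**The case against.** The strongest reply is that the stated analysis ("repeated measures analysis of variance were conducted to determine the relative effectiveness of BATE-G vs. CT-G") is not a single-visit t test. In the group-by-time test, agreement is well short of certain and close to what fully observed data would give, so a match across three outcomes is not empty. This stands. A reader might infer from Step 3 that the match was guaranteed and the check worthless. The documents do not support that for the planned model.

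A second reply is that a smaller ITT than per-protocol estimate is expected, since the two answer different questions. This also stands. A reader might infer that the ITT result is a diluted version of the truth. That holds relative to the observed data, but relative to the true ITT effect Step 5 shows no bias, understatement or overstatement, depending on facts not given.

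Third, the plan discloses the substitution and its intended direction, so it is not concealed. That is fair. What is missing is the size of the shrinkage and the per-protocol estimates.

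Fourth, 28% and 37% missing are planning figures that assume no dropout was assessed. Including dropouts in ITT does not settle this, and payment per assessment is not tied to finishing treatment. The figures must be read as conditional.

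None of this rescues the reporting rule. Even where agreement is not automatic, agreement in significance does not establish agreement in effect.

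**Conclusion.** The point holds as one about reporting and about what the match can show. The per-protocol results are left out on a criterion that cannot detect a difference in effect size and gives little assurance about missing data, because the imputed values carry no information about the dropouts.

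If dropouts are unassessed and losses run at the planned rates equally in both arms, the ITT difference is about 0.72 (post-treatment) and 0.63 (follow-up; 0.61-0.65 over the stated loss range) of the observed-data difference. At a single visit the significance call then almost never differs. In the planned group-by-time test it differs in roughly 5-21% of trials per outcome. The real size cannot be computed, because observed missingness and the per-protocol results are not in the documents.

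ITT is rightly primary. Nothing here shows that its conclusion is wrong, or in which direction it might be.

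**What to change.** Delete the rule that reports ITT alone when significance does not change. For ICG-R, BDI-II and the PTSD scale, report the between-group difference with its 95% confidence interval at each follow-up, for ITT and for per-protocol (at least 5 of 7 sessions), whatever the p-values. Give the number of patients with observed data by arm and visit.

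Do not use the gap between ITT and per-protocol as a measure of robustness, because mean substitution produces part of that gap mechanically. Beside both, show an ITT estimate from the observed data without mean substitution, for example from a likelihood-based mixed model. State whether treatment dropouts were assessed and how gaps inside the per-protocol set were handled.

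The cost is one extra results table and one extra model per outcome. The per-protocol analyses have already been run.
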